#### II.4. How Can Sweet WP Tobacco Additives Contribute to Indirect Harm?

By masking the unpleasant, bitter taste of nicotine, sweet additives play a powerful role in initiation of and addiction to tobacco smoking. Tobacco industry documents reveal that cigarette manufacturers, in an attempt to maximize the appeal of cigarette smoke, conducted human studies to determine the optimal ratio of added sugars to nicotine content. Adding sugars increased the concentration of carbonyls in the smoke, which, as acids, reduced the smoke pH, resulting in nicotine being inhaled predominantly in its protonated form. Protonated nicotine is more appealing for first-time users because it is less harsh than freebase nicotine and is therefore easier to inhale. Nicotine is a highly addictive compound, and WP tobacco

smoking delivers enough nicotine to support nicotine addiction. Moreover, glycerol can enhance the transfer of nicotine to the smoke increasing nicotine delivery to the user, and both glycerol and sugars reduce the harshness and increase the appeal of WP tobacco smoke. There is evidence that WP tobacco smoking may function as a gateway for initiation and regular use of combustible cigarettes.

## II.5 Why Use Investigational Tobacco Products?

Some crossover studies have examined WP tobaccos that contain varying levels of glycerol and presence/absence of characterizing flavors and found differences in smokers puffing behaviors, toxicant exposure and appeal when using these products. However, the measured differences cannot be related to the level of specific additive in those studies because the WP tobacco brands tested had numerous other differences that were not quantified. To systematically examine the direct and indirect harm associated with specific additives it is necessary to precisely fortify the WP tobacco with specific levels of the additives. As the initial raw material for the manipulated tobacco, we will use a popular unflavored WP tobacco with low glycerol content.

To ensure the ITPs are ecologically valid, we will fortify the unflavored WP tobacco with the correct type and concentration of sugars. There is a common belief that WP tobacco is sweetened by adding honey, perhaps because “ma’assel” is taken from the Arabic “muassel,” which means “honeyed”. About 70% of honey is made up of two sugars, glucose and fructose, that are present in roughly equal amounts. Given the low cost of WP tobacco (\$3 for a pack that has the same amount of tobacco as an \$8 pack of cigarettes), and that the worldwide market for it exceeded \$1.9B in 2017, it is more likely that inexpensive syrups are used. Table II.1 shows the sweeteners that comprise honey and sugar, and less expensive syrups such as high fructose corn syrup (HFCS) and molasses, in comparison to the sugar content data we collected on flavored and unflavored WP tobacco. Based on these data, the unflavored WP tobacco may have been sweetened with a combination of sugar, honey and molasses; but molasses and HFCS 55 are the more likely candidates given their availability and low cost. For the flavored WP tobacco, sucrose was not detected and thus neither molasses nor sugar were used. Molasses and HFCS 42 were most likely used to sweeten the flavored WP tobacco, given their availability and low cost. To more precisely isolate the additives of interest, we will fortify the unflavored tobacco with food grade (>99% purity) glycerol, glucose and fructose to produce sweetness and glycerol levels that do not exceed those measured in the flavored tobacco.

TABLE II.1. SUGAR CONTENT OF SWEETENERS, AND FLAVORED AND UNFLAVORED WP TOBACCO.

Sweetener	Hexoses, wt %			Glycerol, wt %
	Sucrose	Glucose	Fructose	
Corn Syrup	-	100	-	-
HFCS 55	-	45	55	-
HFCS 42	-	58	42	-
Honey		32	39	-
Molasses	34	8	8	-
Sugar	99.7	-	-	
Flavored WP Tobacco a	-	30	29	38
Unflavored WP Tobacco a	25	34	37	4

“ - ” = negligible; a = wt % expressed as a fraction of the sum of the primary sweeteners sucrose, glucose, fructose and glycerol.

Not all sugars have the same sweetening power. A sweetness hierarchy for sugars has been determined empirically by asking participants to detect sweetness in progressively increasing concentrations of single sugars. Among the most highly fortified sweeteners added to WP tobacco, sucrose and fructose have the highest relative sweetness. A power function to predict the relative sweetness of sugars based on their concentration and individual sweetening power was determined empirically from human trials. Because the unflavored WP tobacco that is our starting material contains sucrose, it is important to tally the relative sweetness contributions of all the sugars and glycerol in the ITPs to produce medium and high sweetness levels, while also producing medium and high glycerol levels.

Equally important to consider is the nicotine content of each of the proposed ITPs, not only because nicotine can drive use behavior, it also produces the bitterness that the sugars and glycerol are added to offset. Given that the additives can comprise more than half the weight of the WP tobacco, we must normalize the relative sweetness by the nicotine coming from the tobacco leaf itself. We define the term “Starter Product Index” (SPI) to assign a numerical quantity to the mass of sugars fortified in the tobacco to offset the bitter harshness of nicotine:

SPI = sum of the relative sweetness of the sugars and glycerol / mass of nicotine

The proposed additive concentrations in the ITPs are shown in Table II.2. For ecological validity, the SPI of the proposed ITPs are bracketed by the SPIs for the unflavored and flavored commercial WP tobaccos, also shown in Table II.2.

*Table II.2. The proposed Investigational Tobacco Products (ITPs) are fortified with ecologically valid levels of sweet additives.*

	WP Tobaccos	Concentration (mg additive/g of tobacco)				Relative Sweetness	SPI
		Glycerol	Sucrose	Glucose	Fructose		
Proposed ITPs	Medium Glycerol Medium Sugars	60	90	125	135	106	64
	High Glycerol Medium Sugars	120	90	125	135	101	68
	Medium Glycerol High Sugars	60	90	195	225	110	91
	High Glycerol High Sugars	120	90	195	225	103	99
Commercial Products	Unflavored WP Tob	13	90	125	135	106	59
	Flavored WP Tob	246	0	195	190	106	103

## II.6. Why Use a Research-Grade Waterpipe?

Commercially available WPs and their components vary widely in design and durability, including differences in fabrication materials used for stems, bases, bowls, and hoses; sealing joint designs and degree of leak-tight fit; and diameter of flow path. All of these components can affect puffing intensity, and exposure to nicotine, CO and other harmful toxicants. A rugged, reproducible WP is needed to reliably determine the variability in human WP puffing behavior (topography). Our team developed and qualified the use of standardized single- and dual-hose WPs (RWP and RWP2) equipped with puffing topography analyzers. The RWP2 is shown in Figure II.1. The RWPs both operate with known precision and accuracy, and are well-accepted by established WP smokers in terms of satisfaction and reward. More information on the RWP and RWP2 is provided in Appendix A to this protocol.

## II.7. What will this study add?

[figure not shown]
The study design is highly innovative in several ways in that it 1) includes human and machine smoking of a manipulated, ecologically valid WP tobacco product to isolate the effects of glycerol and sugar additives, 2) it draws on a comprehensive set of chemical measurement techniques to estimate ranges of volatile and semivolatile HPHCs delivered to the smoker, and 3) it uses a validated, research grade waterpipe (RWP) of known precision and accuracy. More detail on these study design aspects is given below.

Several studies have used behavioral data and machine smoking to characterize the chemical composition, toxicity, and carcinogenicity of popular WP tobaccos. To the best of our knowledge, this is the first human study to use a precisely manipulated WP tobacco in order to systematically examine the effects of the additives of greatest interest with respect to evaluating direct and indirect harm

associated with WP smoking: glycerol, fructose and glucose. As the initial raw material for the manipulated tobacco, we will use a popular unflavored WP tobacco with low glycerol content (see Table II.2). Our data on the sweet additives measured in a popular flavored and a popular unflavored WP tobacco were used to ensure the identities and concentrations of additives in the ITPs are ecologically valid.

The multi-analyte chemical characterization techniques for the measurement of established and proposed HPHCs have been developed and validated by MPI [name] for use in tobacco regulatory research on WPs. Although the chemical composition of WP tobacco and emissions are important, other factors also contribute to the potential health impacts of WP smoking. The subjective data collection techniques include the application of a food industry-established psychophysical measurement technique to quantify the perceived intensities of tobacco flavors. Moreover, general WP harm perceptions (absolute, relative) and specific health risk perceptions (e.g., addictiveness, lung cancer, oral cancer) will be captured using survey items adapted from the US Population Assessment of Tobacco and Health Study and being used in MPI [name]'s current WP study (R01CA229306). We will also employ either the RWP or RWP2, novel, standardized devices developed by MPI [name] that operate with high precision and accuracy for the measurement of WP puffing behavior for one (RWP) or two

Figure II.1. A research-grade waterpipe (RWP) equipped with human puffing topography data collection.

people (RWP2) smoking from the same WP. The research-grade waterpipe will also be used for the generation of machine-smoked constituent data using both human puffing topography collected in the proposed study, and an accepted standardized, multi-staged puffing regimen derived from a previously examined cohort of experienced WP smokers smoking the RWP and a flavored WP tobacco. The RWP2 was developed from the single hose research-grade waterpipe, the RWP, and is a tool with benchmarked performance metrics that was well-accepted by experienced WP smokers in a previously conducted clinical research. The RWP2 is fabricated from inert materials that do not scavenge, via adsorption to surfaces, nor generate via thermal degradation or off-gassing, the HPHCs of interest being measured in mainstream smoke.

Currently there are no regulations governing the content of WP tobacco. Because mandated changes in tobacco content may lead to unintended consequences that ultimately result in public health declines, human use behaviors must be well understood prior to implementing regulatory product standards. Compensation, or the degree to which a smoker changes their intake of smoke to make up for the changes made to the tobacco product, is one possible unintended consequence. The proposed smoke HPHC yield measurements, made in smoke generated using both a standardized and a specific (to human-use of the tobacco) puffing regimen, along with the participants' plasma nicotine boost from using the product, will allow us to determine if compensation, and thus greater HPHC exposures, is associated with the presence/absence of sweet additives.

This study will be the first to combine powerful analytical chemistry techniques, CO and nicotine biomarkers, cutting edge psychophysical measurement tools, and risk perception instruments to map the relationship between sensory experiences and preferences of sweetness and flavor to specific additive content in WP tobacco that affect these experiences and preferences. The data from the proposed study will provide direct links between WP tobacco's primary additives, CO and nicotine biomarkers, smoker preferences, perceptions of harm and puffing behaviors, and the subsequent range of HPHC exposures associated with these additives and behaviors. This work will inform the FDA regarding its regulatory authorities surrounding the manufacture, distribution and marketing of WPs, and inform the evaluation of product applications and development of product standards, such as glycerol and sugar content, to reduce the resulting public health toll from WP tobacco product use in the US.

## III. Procedures

### III.1. Research Design Overview

The proposed study will include preparing and characterizing the content of 4 investigational tobacco products (ITPs) (Aim 1); characterizing the mainstream smoke toxicant emissions from machine smoking the 4 ITPs using a single, established puffing regimen (Aim 2); measuring human puffing behavior, general harm and specific health risk and flavor perceptions, lung function, and biomarkers of exposure in a group of established WP smokers smoking the 4 ITPs in the laboratory (Aim 3), and estimating toxicant exposure ranges using machine smoking and puffing regimens derived from the human laboratory testing (Aim 4).

### AIM 1

#### III.A1. Aim 1 Research Design

**Characterize the HPHC and sugar content of four WP tobaccos (one brand prepared four different ways to vary glycerol and sugars).** Aim 1 will focus on the preparation and subsequent chemical characterization of WP tobacco with high and medium levels of sugars and glycerol. A commercial WP tobacco will be manipulated to prepare a 2 x 2 matrix of 4 tobaccos with medium and high levels of glycerol and sugars.

#### III.B1. Aim 1 Sample

There are no human participants planned for Aim 1. Sufficient quantities of the commercial WP tobacco for the grant will be purchased at the beginning of the study by a single vendor and stored in sealed containers at room temperature.

#### III.C1. Aim 1 Measurement/Instrumentation

Nicotine, humectants, sugars, carbonyls, and semivolatile furans, as detailed in Table III.3, will be determined twice: once at the beginning and once at the end of the human study. Nicotine content of the unburned tobaccos will be determined using gas chromatography with mass spectral detection (GC-MSD). Humectant content will be determined using GC with flame ionization detection (FID), or GC/MS. Sugar content, including sucrose, glucose, and fructose, will be determined using high performance liquid chromatography (HPLC) techniques. Carbonyls will be determined in the tobacco as their 2,4-dinitrophenylhydrazine (DNPH) derivatives using liquid chromatography tandem mass spectrometry. Semivolatile furans will be determined in the tobacco using a liquid chromatography method previously used by our team.

Total aerobic microbial and total yeast and mold counts (TAMC and TYMC) will be determined according to USP 61, after the ITPs are prepared, midway through participant processing, and at the completion of participant processing.

### III.D1. Aim 1 Detailed Study Procedures

Selection of WP Tobacco. As the starting material for the preparation of the four test tobaccos, we will use a popularly smoked unflavored tobacco (see Unflavored Tobacco in Table II.2) claimed by the manufacturer to “present a plain molasses flavor.” This tobacco has a low glycerol content that is amenable to the proposed product manipulation.

Preparation of WP Tobacco. A popular, commercially available WP tobacco brand (Moassel Saloum) will be prepared four different ways:

- (1) Medium glycerol (60 mg/g), Medium Sugars (350 mg/g)
- (2) High glycerol (120 mg/g), Medium Sugars (350 mg/g)
- (3) Medium glycerol (60 mg/g), High sugars (510 mg/g)
- (4) High glycerol (120 mg/g), High sugars (510 mg/g)

Several packages of the tobacco, purchased from the same source, will be combined, twigs and sticks removed, homogenized, and split into four equal batches. Food grade glycerol, glucose and fructose (>99% purity) will be added to the tobacco to obtain the concentrations shown for the ITPs in Table II.2.

Determination of Nicotine Content. To aid in determining if humectant levels affect the transfer of nicotine from the tobacco into the mainstream smoke, the nicotine content of Batches 1-4 will be individually determined using a method previously qualified by our team. An aliquot (0.25 g) of each tobacco sample will be extracted individually for four hours in a mixture of isopropyl alcohol, methyl tert-butyl ether, and sodium hydroxide using an orbital shaker table at 160 rpm. The extraction solvent mixture will contain a known quantity of quinoline as the internal standard (IS). An aliquot of the extract will be quantitated for total nicotine using gas chromatography with mass spectral detection (GC-MSD).

Determination of Humectant Content. To aid in determining the fraction of humectants transferred to the mainstream smoke and verify the levels of added glycerol, the glycerol and propylene glycol content of each tobacco preparation will be determined using a Health Canada method adopted for use on WP tobacco by Schubert et al.

Determination of Sugars in the Four Tobacco Preparations. The sugar content of the four prepared batches will be quantified. An aliquot (1 g, 3 replicates) of each tobacco preparation will be extracted into HPLC grade water and analyzed using validated methods based on standard liquid chromatography (LC) techniques.

Determination of Carbonyl Content. To determine the fraction of carbonyls in the tobacco vs. those generated as a result of additives, carbonyls will be determined in the tobacco as their 2,4-dinitrophenylhydrazine (DNPH) derivatives using liquid chromatography tandem mass spectrometry.

Determination of Semivolatile Furan Content. To determine the fraction of semivolatile furans in the tobacco vs. those generated as a result of additives, semivolatile furans will be determined in the tobacco using a liquid chromatography method previously used by our team.

Determination of Aerobic Bacteria, Yeast and Mold. Because sugars and glycerol can function as preservatives in WP tobacco, it is important to document the storage stability of the ITPs. Therefore, the total aerobic microbial and total yeast and mold counts (TAMC and TYMC) will be determined according to USP 61, after the ITPs are prepared, midway through participant processing, and at the completion of participant processing.

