## VII. Data Analysis

### VII.1 Analysis Plan

The main research questions from the four Aims in the proposed study have the same structure for data analysis. That is, there are differences attributable to the four tobaccos in the means of the outcome measures of interest. All relevant outcome variables will be first examined with exploratory/descriptive statistical analyses that focus on describing and understanding patterns and distributions for all relevant measures (e.g., tobacco chemical content, mainstream smoke constituents, spirometry measures, topography measures, psychophysical ratings) by the four tobaccos. We will identify any potential outliers, assess distributional assumptions, and apply appropriate transformations to the outcome variables (e.g., log-transformation) if the normality assumption is violated.

For each of the four aims, the following pairwise comparisons will be performed:

$$H0i j: \mu_i = \mu_j \text{ vs. } H1i j: \mu_i \neq \mu_j$$

where  $\mu_i$  = mean target outcome for tobacco type i, and  $\mu_j$  = mean target outcome for tobacco type j. In Aims 1, 2, and 4, the data will be analyzed using one-way ANOVA models for independent outcome data and Tukey's method will be used to control type-I error rate across the six multiple comparisons. A different analysis strategy will be used in Aim 3 due to the clustered study design: participants will complete four different smoking sessions. Thus, in order to account for the hierarchical design, the data in Aim 3 will be analyzed using linear mixed models containing random subject effects. Since linear mixed models allow for incomplete data (e.g.,

due to dropout), data from all completed smoking sessions will be used in the analysis. As in the other aims, Tukey's method will be used to adjust for multiple comparisons of the tobacco treatments in Aim 3. In addition, for Aim 3, we will use linear mixed models to examine the relationships between the perceived sensory intensity ratings and the liking/disliking ratings for a given tobacco preparation.

Integrating results from Aims 1, 2 and 4 with Aim 3 of the study, the absence or presence, or exposure level of certain HPHCs and other chemical compounds across the different tobacco preparations will be mapped with the data on perceived sensory intensity such as sweetness and liking/disliking ratings.

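### Aim 1 is meant to confirm that glycerol (and, by implication, glucose and fructose) reaches and matches its set levels, but its only inferential analysis tests whether the tobaccos are equal

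*Combined protocol and SAP*

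**What the plan says.** Section II.5 argues that, to study specific additives, "it is necessary to precisely fortify the WP tobacco with specific levels of the additives". Section III.A1 sets out to "prepare a 2 x 2 matrix of 4 tobaccos with medium and high levels of glycerol and sugars". By that layout, tobaccos 1 and 3, and 2 and 4, should have the same glycerol; tobaccos 1 and 2, and 3 and 4, should have the same sugars.

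Section III.D1 says that glycerol, glucose and fructose are "added to the tobacco to obtain the concentrations shown for the ITPs in Table II.2". The humectant assay is there in part to "verify the levels of added glycerol, the glycerol and propylene glycol content of each tobacco preparation will be determined". For sugars the wording is weaker: "The sugar content of the four prepared batches will be quantified", from 3 replicates per preparation.

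Section VII.1 starts with descriptive statistics by tobacco, and tobacco chemical content is among its examples. It then states: "For each of the four aims, the following pairwise comparisons will be performed". The null hypothesis is equality of two tobacco means. Aims 1, 2 and 4 use one-way ANOVA with Tukey's method over the six pairs. Section VII.2 plans 4 replicates per preparation, assuming a CV of 20% and log-normal outcomes.

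Neither section gives a comparison with a Table II.2 level, a tolerance, or a criterion for two batches being the same.

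**The concern.** For an additive set by design there are two questions: is each batch at its intended level, and do the batches sharing a level agree? A test of equality between tobaccos answers neither.

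- **Batches made to differ** (medium against high): the null is false by construction, so rejecting it does not show that either level was reached.
- **All batches off by the same factor**: every ratio between tobaccos is unchanged, so every test behaves as if the targets had been met.
- **Batches made to match**: a non-significant difference is not evidence of a match, and no margin says how close is close enough.

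The 2 x 2 matrix separates glycerol from sugars only if shared levels really are shared. The Objectives say the results should inform possible maximum limits for additives. Any such limit needs effects tied to concentrations actually present in the tobacco.

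**Working it through.** **Inputs.** From VII.2: CV 20%, log-normal, 4 replicates, two-sided alpha 0.0083, two-fold change. From III.D1: 3 replicates for sugars; glycerol 60 and 120 mg/g. From VII.1: Tukey, four groups. My assumptions: CVs of 10% and 5%, the sizes of the misses, and independent replicates. The documents give no assay-specific CV.

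**1. The plan's own figure.** Log-scale SD = sqrt(ln(1 + 0.20²)) = 0.198. SE of a difference = 0.198 × sqrt(2/4) = 0.140. Noncentrality = ln 2 / 0.140 = 4.95. With a two-sample t-test on 6 df, power is 80.0%. The stated 80% is reproduced.

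**2. The planned Tukey test.** With 4 × 3 = 12 error df, the critical value on the t scale is 2.97. For 60 against 120 mg/g, power is 96%.

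**3. A common miss.** If both batches are at 70% of target (42 and 84 mg/g), the difference is ln(84/42) = ln 2, the same as on target. The rejection rate stays at 96%.

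**4. A miss in one batch.** If the high batch is made at 90 mg/g and the medium batch is on target, the ratio is 1.5. The test still rejects 50% of the time at CV 20% and 99% at CV 10%, although the high level was not reached.

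**5. A mismatch within a level.** Noncentrality = ln(1.2) / (SD × sqrt(2/n)). For n = 4 and CV 20% this is 0.182 / 0.140 = 1.30. Chance of detecting a 20% mismatch:

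| CV | n = 4 | n = 3 |
|---|---|---|
| 20% (plan) | 8% | 6% |
| 10% (assumed) | 39% | 25% |
| 5% (assumed) | 97% | 86% |

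At CV 20% and n = 4, the mismatch must reach 1.72-fold before power is 80%.

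**6. What intervals would give.** 90% CI factor for a matched ratio = exp(t(0.95) × SD × sqrt(2/n)). For n = 4 and CV 20%: exp(1.782 × 0.140) = 1.28. For n = 3 (8 df): exp(1.860 × 0.162) = 1.35. At n = 4 it is 1.13 at CV 10% and 1.06 at CV 5%. The 95% CI factor for one batch's geometric mean, with n = 4, is 1.24, 1.11 and 1.06 at the three CVs.

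**7. Sucrose.** Table II.2 lists 90 mg/g in the starting tobacco and in all four products, but III.D1 adds no sucrose. Assume the table is per gram of finished product. The starter's mass other than glycerol, glucose and fructose is 1000 − 13 − 125 − 135 = 727 mg/g. In the products it is 680, 620, 520 and 460 mg/g. Sucrose becomes 90 × 680/727 = 84, then 77, 64 and 57 mg/g.

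The table's SPI is relative sweetness divided by nicotine, so it implies nicotine of 106/64 = 1.66 in tobacco 1 and 103/99 = 1.04 in tobacco 4. That fits dilution but does not settle the basis. The 350 and 510 mg/g sugar totals include the 90 (90 + 125 + 135; 90 + 195 + 225), so they depend on it too.

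**The case against.** The strongest reply is that Aim 1 sets out to characterize the tobaccos and, unlike Aims 2 to 4, has no hypothesis. A glycerol mean of 42 against a nominal 60 would be plain in the descriptive table. That stands in part, and it rules out several stronger readings that a reader might infer:

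- **That Aim 1 is analysed only by tests.** VII.1 also plans descriptive statistics. What they lack is a target, a tolerance or an interval.
- **That the plan states a verification duty for every additive.** It does so for glycerol only. For glucose, fructose and matching within a level, the need is inferred from Table II.2 and the 2 x 2 layout.
- **That Tukey tests usually miss a mismatch.** This depends on the CV. The 20% covers Aims 1, 2 and 4 together and is called somewhat conservative; at 5% with 4 replicates, a 20% mismatch is nearly always found.
- **That Aims 2 to 4 would attribute effects to the wrong concentrations.** Nothing obliges those aims to rely on nominal labels, and III.D1 uses measured humectant content for the fraction transferred to smoke. A common proportional miss also keeps the two-fold glycerol contrast, so it affects the labels more than the comparison between tobaccos.

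A further fair point is that a formal equivalence test would do little at CV 20%. With an assumed margin of 1.25 and 4 replicates, it has 6% power when the batches truly match; 12 replicates give 72% and 16 give 87%. The intervals should therefore be read as estimates, not as a pass/fail test.

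**Conclusion.** The concern holds in a limited form. For additives whose levels are set by design, the only inferential analysis in Aim 1 asks the wrong question, and the descriptive statistics are not linked to the levels they would need to confirm. The absence of a target and the invariance to a common miss are logical points that hold at any CV. The detection rate for a within-level mismatch does depend on the CV: about 8% (n = 4) or 6% (n = 3) for a 20% mismatch at the plan's figure, and 39% or 97% with 4 replicates if the CV is 10% or 5%. The 20% mismatch is an illustrative size. The documents do not show that any batch will miss its level. The sucrose figures rest on an assumption about the basis of Table II.2.

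**What to change.** In VII.1, for glycerol, glucose and fructose (and total sugars once the Table II.2 basis is clear), replace the Aim 1 pairwise tests with:

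1. each batch's geometric mean as a percent of its Table II.2 level, with a 95% CI; and
2. the ratio of the two batches sharing a level, with a 90% CI.

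Read both against a tolerance fixed in advance from the assay's known precision. Keep the pairwise tests for constituents not set by design, such as carbonyls and furans. Report measured concentrations beside the labels in Aims 2 to 4.

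State whether Table II.2 is per gram of finished product. Report sucrose as a measured value, not against a target. Reconcile the 3 sugar replicates in III.D1 with the 4 per preparation in VII.2.

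The cost is mainly SAP wording, with the same assays. The downside is precision: if the CV really is 20%, a matched ratio is known only to within a factor of about 1.28 (n = 4) or 1.35 (n = 3), and verification may be inconclusive unless replicates are added.

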## VII.2. Sample Size Justification.

Since Aims 1, 2, and 4 do not involve human subjects, we expect low variability across replicates. Thus, assuming a somewhat conservative coefficient of variation (CV) of 20% and log-normal outcomes, a total of **4 replicates per tobacco preparation** will provide 80% power to detect a two-fold change in the geometric means of two groups at a conservative two-sided Bonferroni-corrected type-I error rate of 0.0083.

Our sample size for Aim 3 was selected to ensure that we have adequate power to detect moderate effect sizes in our comparisons of topography outcomes. We made the following assumptions for the power analysis:

- Based on the intravariability data analysis for the RWP, correlation coefficients within subjects ( $r$ ) were assumed to be 0.6, 0.7 or 0.8.
- Small, medium, and large effect sizes ( $d$ ) of 0.2, 0.5, and 0.8 standard deviations.
- A two-sided, Bonferroni corrected type-I error rate of 0.0083.

Our power analysis, summarized in Table VII-5, revealed that a sample size of 43 subjects will provide over 80% power to detect a moderate effect size unless the within pair correlation is high (0.2 or 0.3) and the within participant correlation is modest (0.6). However, since this power analysis assumes complete follow-up, we will recruit **60 participants** to account for a possible attrition rate of 20%, and ensure the Latin square ordering is balanced across the four tobacco types.

Table VII.5. Estimated % power to for pairwise comparisons of tobacco preparations based N = 25 pairs (50 subjects).

$r$	$\rho$	Power		
		$d=0.2$	$d=0.5$	$d=0.8$
0.6	0.1	0.108	0.803	0.998
	0.2	0.097	0.759	0.996
	0.3	0.088	0.717	0.994
0.7	0.1	0.153	0.918	> 0.999
	0.2	0.138	0.889	> 0.999
	0.3	0.125	0.857	0.999
0.8	0.1	0.255	0.989	>0.999
	0.2	0.228	0.981	>0.999
	0.3	0.207	0.971	>0.999

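### The Aim 1 sugar assay is set at 3 replicates, but the 80% power statement covering Aim 1 rests on 4 per preparation; the two sections need to be reconciled

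*Combined protocol and SAP*

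**What the plan says.** The sample size section (VII.2) treats the three laboratory aims together: "Since Aims 1, 2, and 4 do not involve human subjects, we expect low variability across replicates". It sets the size at "4 replicates per tobacco preparation" and says that this "will provide 80% power to detect a two-fold change in the geometric means of two groups", "assuming a somewhat conservative coefficient of variation (CV) of 20% and log-normal outcomes", "at a conservative two-sided Bonferroni-corrected type-I error rate of 0.0083". No assay is excepted.

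The Aim 1 procedures (III.D1, on determining sugars) give another number: "An aliquot (1 g, 3 replicates) of each tobacco preparation will be extracted into HPLC grade water". Of the content assays described in III.D1, only this one states a replicate number.

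Two other sections bear on the point. The Aim 1 measurement section (III.C1) says that the content analytes, sugars among them, "will be determined twice: once at the beginning and once at the end of the human study". The analysis plan (VII.1) specifies one-way ANOVA over the four tobaccos for Aims 1, 2 and 4, and "Tukey's method will be used to control type-I error rate across the six multiple comparisons".

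The designed total sugar levels are 350 mg/g (medium) and 510 mg/g (high), in Objectives and III.D1.

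**The concern.** Tobacco chemical content is among the measures listed in VII.1, and the pairwise comparisons there apply to all four aims. The sugar assay therefore falls within the 80% statement, yet its replicate number is below the one on which that statement rests. With so few replicates, one fewer matters: error degrees of freedom in a two-group comparison fall from 6 to 4.

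Sugar is one of the two factors that define the 2 x 2 set of tobaccos. The Aim 1 measurements are the evidence on how far the medium and high sugar products differ in practice, and the sugar contrasts in Aims 3 and 4 are read against them. A reader should be able to tell how many sugar values per product enter the comparison and what power follows. At present the sections give two different answers.

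**Working it through.** **Inputs.** From VII.2: ratio of geometric means 2, CV 20%, log-normal outcome, two-sided alpha 0.0083 (0.05/6), n = 4. From III.D1: n = 3 for sugars. From VII.1: four groups, Tukey adjustment over six comparisons.

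**Formulas.**
- Log-scale SD: s = sqrt(ln(1 + CV²)) = sqrt(ln 1.04) = 0.198.
- Noncentrality for a pairwise comparison: ncp = ln(ratio) / (s × sqrt(2/n)).
- Power is the probability that a noncentral t variable exceeds the critical value; the opposite tail is negligible here. Degrees of freedom are 2(n − 1) for two groups alone and 4(n − 1) with error pooled over the four tobaccos. The Tukey critical value is the 95% studentized-range quantile for four groups divided by sqrt(2).

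**Reproducing the plan's figure.** With n = 4, ncp = 0.693 / (0.198 × 0.707) = 4.95. On 6 df the critical value at alpha 0.0083 is 3.87, and power is 0.80. This matches the stated 80% and identifies the calculation as a two-group t-test.

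**Changing only n to 3.** ncp = 0.693 / (0.198 × 0.816) = 4.29. On 4 df the critical value is 4.86, and power is 0.46. The ratio detectable with 80% power rises from 2.00 to 2.71.

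**Two-fold change, CV 20%, by method:**

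| Method | n = 3 | n = 4 |
|---|---|---|
| Two groups, alpha 0.0083 (reproduces VII.2) | 0.46 | 0.80 |
| Pooled ANOVA error, alpha 0.0083 | 0.76 | 0.94 |
| Pooled ANOVA error, Tukey (planned in VII.1) | 0.82 | 0.96 |

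**Two assay occasions.** If 3 replicates are run at each occasion and all are pooled as independent, n = 6 and the two-group method gives 0.99. The documents do not say whether either condition holds.

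**The designed sugar contrast.** 510/350 = 1.457, which is smaller than two-fold. VII.2 gives a single CV of 20% for all assays; the lower CVs below are assumptions that show the range.

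| Assay CV | Two groups, n = 3 | Two groups, n = 4 | Tukey, n = 3 | Tukey, n = 4 |
|---|---|---|---|---|
| 20% | 0.12 | 0.25 | 0.27 | 0.43 |
| 15% | 0.23 | 0.47 | 0.50 | 0.72 |
| 10% | 0.53 | 0.86 | 0.88 | 0.98 |
| 7.5% | 0.80 | 0.99 | 0.99 | >0.99 |

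At CV 20%, the two-group method needs 9 replicates for 80% power at this contrast.

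**The case against.** The strongest reply is that the planned analysis is not short of power. VII.1 specifies ANOVA with Tukey's method, and under it 3 replicates still give 82% for a two-fold change at CV 20%. The figure of 46% belongs to a two-group Bonferroni test that will not be used and whose error rate VII.2 itself calls conservative. This stands. A reader might infer from 46% that Aim 1 is underpowered for sugars against its two-fold target; the documents do not support that.

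Second, sugars are measured on two occasions, so as many as 6 values per preparation may be available. This stands as a possibility only. A comparison of start with end of study would be a reason to keep the occasions apart.

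Third, VII.2 expects low variability and regards 20% as somewhat conservative, and the sugar levels are set by adding ingredients of more than 99% purity. The assay largely checks a known formulation, so the practical loss is probably small. This is fair, though the documents give no CV specific to the sugar assay.

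Fourth, the 1.46-fold figures might be read as showing that the missing fourth replicate is what puts the designed contrast at risk. They do not: at CV 20%, 4 replicates give only 0.25, or 0.43 with Tukey. Those figures are a reason to give sugars their own power statement, not evidence that going from 3 to 4 is enough.

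None of this removes or explains the difference between the two sections.

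**Conclusion.** The plan is inconsistent on a stated size: 4 replicates per preparation in VII.2, 3 for sugars in III.D1. The 80% figure is not miscalculated; it reproduces with 4. For sugars, however, the size behind it is not the one planned. Against the plan's stated calculation, 3 replicates give 46% (76% with pooled error). Against its planned Tukey ANOVA they give 82%, compared with 96% for 4.

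These results assume a two-fold change, a CV of 20%, independent log-normal replicates and a single occasion of 3. A lower assay CV, or pooling of the two occasions, would shrink the practical effect, probably to little. This is a minor point, worth correcting because correction is nearly free.

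**What to change.** Reconcile III.D1 with VII.2 in one of two ways.

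1. Set the sugar assay at 4 replicates. If the present 3 are per occasion, this costs one more aliquot per product per occasion: 4 products × 2 occasions = 8 aliquots in all.
2. Keep 3, exempt sugars from the 80% statement, and give sugars their own power figure based on the planned Tukey test, the designed 1.46-fold contrast (350 v 510 mg/g) and a CV taken from the sugar assay itself. This costs wording and one short calculation.

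The second option also deals with the gap between the two-fold target and the designed contrast, which the first leaves open.

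Under either option, state whether the replicate number applies at each occasion, and whether the start and end values are pooled or analysed separately. No participant procedure changes.
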